## ORAL INSULIN FOR NAFLD/NASH

The similarities between type 2 DM and NAFLD/NASH in risk factors, pathogenic mechanisms and complications suggest common approaches to therapeutic intervention. Recall that 70% of type 2 DM patients will develop NAFLD/NASH and that 85% of new cases of diabetes will be type 2 patients. The key component of insulin resistance shared by diabetes and NAFLD/NASH makes direct insulin intervention an attractive option. The oral insulin formulation has the potential advantage of first pass metabolism in the liver allowing local availability and concentration of insulin at the affected liver fat cells.

## ORAL INSULIN DEMONSTRATIONS OF EFFICACY IN TYPE 2 DIABETES

Oramed's research and development team has performed multiple studies on pigs and canines over the last decade. The studies were designed to optimize the composition and functionality of our oral insulin modality and to demonstrate its safety and efficacy for use in animals and humans.

## **2 STUDY OBJECTIVES AND ENDPOINTS**

### **2.1 Primary Objective**

- To evaluate the safety of oral insulin in patients with nonalcoholic steatohepatitis (NASH) and type 2 DM.

### **2.2 Secondary Objective**

- To assess whether oral insulin may be effective in reducing liver fat content and inflammation in patients with NASH and type 2 DM.

### **2.3 Primary Endpoint**

- To evaluate safety of ORMD-0801 in patients with nonalcoholic steatohepatitis (NASH) and type 2 DM.

### **2.4 Secondary Endpoint**

- To evaluate the effectiveness of ORMD-0801 in reducing liver fat content in patients with NASH and type 2 DM by measuring the final and baseline differences in the MRI-PDFF.

### 3 INVESTIGATIONAL PLAN

#### 3.1 Overall Study Design and Plan

This is a double-blind, randomized, placebo-controlled, multi-center study using the oral ORMD-0801 insulin formulation in patients with NASH and confirmed type 2 DM. This exploratory multi-center study will enroll patients with NASH and type 2 DM between the ages of 18 and 70. Subjects will undergo a Screening Phase up to 42 days prior to the Treatment Phase, a Placebo Run-in Phase for 2 weeks, a Treatment Phase for 12 weeks and an End-of-Study Phase 4 weeks after completion of the Treatment Phase. Approximately 36 subjects will be randomized in a 2:1 ratio to receive either 8 mg ORMD-0801, 1 capsule twice a day (once in the morning approximately 30 to 45 minutes prior to breakfast and no later than 10 AM, and once at night between 8 PM to Midnight and no sooner than 1 hour after dinner) or matching placebo.

At Screening (Visit 1, up to week -6), subjects will sign the ICF and inclusion and exclusion criteria will be reviewed. Medical history, demographics (sex, age, race and ethnicity), and prior and concomitant medications will be recorded. Height and weight will be measured, and BMI will be calculated. Vital signs (SBP/DBP, heart rate and oral temperature), complete physical examination, 12-Lead ECG, clinical laboratory evaluations, serum pregnancy test for females of childbearing potential, blood lipids test, HbA1c, viral serology, CAP-Fibroscan and MRI-PDFF will be performed. For females of non-childbearing potential, FSH levels will be tested if results are not available. Adverse events will be monitored and recorded.

After Screening, each subject will undergo a Placebo Run-in Phase (Visit 2, to Week -2). Concomitant medications will be reviewed. All subjects will receive the morning treatment (Run-in Placebo) in clinic, 1 bottle of placebo medication and subject diaries will be dispensed. Vital signs (SBP/DBP, heart rate and oral temperature) and weight will be collected. Fasting blood glucose and fasting insulin will be measured, urine pregnancy test will be performed for females of childbearing potential. Self-monitored fasting morning blood glucose (finger-stick) will be recorded in the patient diaries 3 days weekly in the morning. Adverse events will be monitored and recorded.

Subjects will then undergo a Treatment Phase consisting of a treatment period of 12 weeks that will start at Visit 3 (Week 0) and outpatient visits at Weeks 1, 2, 4, 8, and 12 (final visit). At each visit, concomitant medication will be reviewed, weight will be measured, and sufficient quantity of medication will be dispensed to last until the next nominal clinic visit. Medication compliance check will be performed, self-monitored fasting morning blood glucose (finger-stick) will be recorded 3 days weekly in the morning and subjects' diaries will be reviewed. Vital signs (SBP/DBP, heart rate and oral temperature) will be recorded. Adverse events will be monitored and recorded. ORMD-0801 morning treatment will be administered in clinic during Visits 3, 6 and 7.

At Visit 3, urine pregnancy test will be performed for females of childbearing potential. At Visit 8, subjects will have HbA1c evaluations and MRI-PDFF performed. At Visits 3 and 8, a complete physical exam and CAP-Fibroscan will be performed.

At Visits 3 (baseline), 6, 7, and 8, patients will have clinical laboratory evaluations (serum chemistry, hematology) and blood lipids performed. Fasting blood glucose, insulin (also used for HOMA estimates) and adiponectin levels will be measured.

The End-of-Study (EOS) Visit (Visit 9) will be conducted 4 weeks following the last scheduled treatment visit. Subjects concomitant medications will be reviewed, and weight will be measured. A complete physical exam and ECG will be performed and vital signs (SBP/DBP, heart rate and oral temperature) will be measured if deemed necessary by the investigator. Clinical laboratory evaluations [serum chemistry (including liver function tests (LFTs) and blood lipids) and hematology] will be performed. Fasting blood glucose, fasting insulin, HbA1c and adiponectin levels will be measured. Subject diaries will be collected and reviewed for self-monitored fasting morning blood glucose. Adverse events will be monitored and recorded. Subjects who are discontinued early from the study will complete the EOS evaluations at the time of early discontinuation.

### **3.2 Screening/Visit 1 (up to Week -6, up to -42 Days)**

At the Screening Visit, potential subjects will be given a detailed oral presentation describing the nature, purpose, risks, and requirements of the study and will receive detailed written information. Subjects will be given ample time to consider participation and ask questions which will be adequately addressed by site personnel.

Once the subject is satisfied that he/she is willing to participate in the study, he/she will be asked to sign the study informed consent form (ICF) (refer to [Section 11.1.4](#) for further detail regarding the ICF). The investigational site personnel obtaining written consent from the subject will also sign the form to confirm consent has been obtained.

Once signed, the Investigator will retain the original ICF for the subject's study records and provide the subject with a signed copy. The investigator will verify that informed consent has been obtained from each subject prior to enrollment into the study and prior to the subject undergoing any study-related procedures.

Screening process will take place at Visit 1, up to 42 days prior to the treatment phase. Subjects will report to the clinic in the morning following a 10-hour fast. Screening activities after obtaining informed consent will be conducted and will consist of the following:

#### **3.2.1 Screening/Visit 1 (up to Week -6, up to Days -42)**

- Review inclusion and exclusion criteria;
- Completion of medical and social history, including tobacco, alcohol, caffeine, and drug use;
- Collection of demographic data (sex, age, race and ethnicity);
- Review of prior and concomitant medication;
- Complete physical examination (PE);
- Height and weight will be measured, BMI will be calculated;
- 12-lead electrocardiogram (ECG);
- Measurement of vital signs (SBP/DBP, heart rate and oral temperature);

- Collection of fasted blood samples for clinical laboratory evaluations (see [Section 6.5.5.1](#) for a complete list of tests performed):
  - Serum Chemistry including liver function tests (LFTs), blood lipids, and Thyroid Stimulating Hormone (TSH);
  - Hematology;
  - HbA1c;
  - Viral serology (HCV-Ab, HBsAg, HBcore-total, HBs Ab, and anti-HIV Ab);
  - Serum pregnancy test (women of childbearing potential/WCBP only);
- Serum FSH (to test for women in post menopause, if not available);
- CAP - Fibroscan;
- MRI-PDFF;
- AE/SAE assessment.

For subjects who meet eligibility criteria based on the Screening assessments, instruction will be provided on the following:

- the use of adequate contraceptive methods (see [Section 4.1](#)) for the duration of the study (Screening through End-of-Study (Visit 9));
- minimal use of concomitant medications during the study, if possible, and avoid prohibited medications as defined in [Section 5.6](#);
- maintenance of usual dietary habits and avoidance of drastic changes, such as a conversion to a vegetarian diet;
- restraint from excessive alcohol use or binge drinking during the study, and restraint from drinking alcohol from 72 hours prior to all study visits;
- restraint from excessive caffeine use (i.e., more than five cups of caffeinated beverages per day) during the study.

### 3.2.2 Screen Failure

A screen failure is defined as a subject who has signed the ICF, does not meet all the entry criteria outlined in [Section 4](#) of this protocol. Note that this includes assessments through Visit 1 (up to Days -42), prior to receiving IMP.

The Investigator is responsible for keeping a record of all subjects screened for entry into the study and subsequently excluded. The reason(s) for exclusion will be recorded in the source documents and on the Screening log.

## 3.3 Placebo Run-in Phase/Visit 2 (Week -2, Days -14)

The Placebo Run-in Phase will consist of a 2-week period starting at Visit 2 (Week -2). Subjects will report to the clinic in the morning following a 10-hour fast prior to taking morning medication. The following procedures will be performed:

### 3.3.1 Visit 2 (Week -2)

- Review of concomitant medication;
- Measurement of weight;
- Urine pregnancy test (women of childbearing potential/WCBP only) prior to dosing;

- Dispense 1 bottle of placebo with instructions for administration. Subjects will receive placebo 8 mg (1 x 8 mg capsule) administered twice daily, once in the morning approximately 30 to 45 minutes prior to breakfast and no later than 10AM, and once at night between 8 PM to Midnight and no sooner than 1 hour after dinner;
- Measurement of vital signs (SBP/DBP, heart rate and oral temperature);
- Measurement of fasting blood glucose and fasting insulin for HOMA estimates;
- Diaries will be dispensed for each week for subjects to self-monitor fasting morning blood glucose;
- Self-monitored fasting morning blood glucose (finger-stick) recorded in the patient diaries 3 days weekly in the morning;
- AEs/SAEs assessment;
- Subjects will be administered morning placebo medication in clinic followed by a small snack after 30 to 45 minutes;
- Remind subjects to arrive fasting for Visit 3 in 2 weeks.

### 3.4 Treatment Phase (Week 0, Visit 3 – Week 12, Visit 8)

The Treatment Phase will consist of a 12-week treatment period.

#### 3.4.1 Visit 3 (Week 0, Days 0±4)

Subjects will report to the clinic in the morning following a 10-hour fast prior to taking morning medication. The following procedures will be performed:

- Review of concomitant medication;
- Complete physical examination;
- Measurement of weight;
- Collection of unused placebo medication;
- Dispense 1 bottle of ORMD-0801 medication with instructions for administration. Subjects will receive either 8 mg ORMD-0801, 1 capsule twice a day (once in the morning approximately 30 to 45 minutes prior to breakfast and no later than 10 AM, and once at night between 8 PM to Midnight and no sooner than 1 hour after dinner) or matching placebo;
- Perform medication compliance check;
- Measurement of vital signs (SBP/DBP, heart rate and oral temperature)
- Collection of fasted blood samples for clinical laboratory evaluations (see [Section 6.5.5.1](#) for a complete list of tests performed):
  - Serum Chemistry including liver function tests (LFTs) and blood lipids;
  - Hematology;
- Urine pregnancy test (women of childbearing potential/WCBP only) prior to active dosing;
- Measurement of fasting blood glucose and fasting insulin for HOMA estimates;
- Review/Dispense diaries for each week for subjects to self-monitor fasting morning blood glucose;
- Self-monitored fasting morning blood glucose (finger-stick) recorded in the patient diaries 3 days weekly in the morning;
- Adiponectin test;

- CAP-Fibroscan;
- AEs/SAEs assessment;
- Subjects will be administered morning treatment dose in clinic followed by a small snack after 30 to 45 minutes;
- Remind subjects to arrive for Visit 4 in 1 week.

#### 3.4.2 Visit 4 (Week 1, Days 7±4)

Subjects will report to the clinic in the morning and the following procedures will be performed:

- Review of concomitant medication;
- Measurement of weight;
- Collection of unused ORMD-0801 medication;
- Dispense 1 bottle of ORMD-0801 medication with instructions for administration. Subjects will receive either 8 mg ORMD-0801, 1 capsule twice a day (once in the morning approximately 30 to 45 minutes prior to breakfast and no later than 10 AM, and once at night between 8 PM to Midnight and no sooner than 1 hour after dinner) or matching placebo;
- Perform medication compliance check;
- Measurement of vital signs (SBP/DBP, heart rate and oral temperature);
- Review/Dispense diaries for each week for subjects to self-monitor fasting morning blood glucose;
- Self-monitored fasting morning blood glucose (finger-stick) recorded in the patient diaries 3 days weekly in the morning;
- AEs/SAEs assessment;
- Remind subjects to arrive for Visit 5 in 1 week.

#### 3.4.3 Visit 5 (Week 2, Days 14±4)

Subjects will report to the clinic in the morning following procedures will be performed:

- Review of concomitant medication;
- Measurement of weight;
- Collection of unused ORMD-0801 medication;
- Dispense 1 bottle of ORMD-0801 medication with instructions for administration. Subjects will receive either 8 mg ORMD-0801, 1 capsule twice a day (once in the morning approximately 30 to 45 minutes prior to breakfast and no later than 10 AM, and once at night between 8 PM to Midnight and no sooner than 1 hour after dinner) or matching placebo;
- Perform medication compliance check;
- Measurement of vital signs (SBP/DBP, heart rate and oral temperature);
- Review/Dispense diaries for each week for subjects to self-monitor fasting morning blood glucose;
- Self-monitored fasting morning blood glucose (finger-stick) recorded in the patient diaries 3 days weekly in the morning;
- AEs/SAEs assessment;

- Remind subjects to arrive fasting for Visit 6 in 2 weeks.

#### 3.4.4 Visit 6 (Week 4, Days 28±4)

Subjects will report to the clinic in the morning following a 10-hour fast prior to taking morning medication. The following procedures will be performed:

- Review of concomitant medication;
- Measurement of weight;
- Collection of unused ORMD-0801 medication;
- Dispense 2 bottles of ORMD-0801 medication with instructions for administration. Subjects will receive either 8 mg ORMD-0801, 1 capsule twice a day (once in the morning approximately 30 to 45 minutes prior to breakfast and no later than 10 AM, and once at night between 8 PM to Midnight and no sooner than 1 hour after dinner) or matching placebo;
- Perform medication compliance check;
- Measurement of vital signs (SBP/DBP, heart rate and oral temperature);
- Collection of fasted blood samples for clinical laboratory evaluations (see [Section 6.5.5.1](#) for a complete list of tests performed):
  - Serum Chemistry including liver function tests (LFTs) and blood lipids;
  - Hematology;
- Measurement of fasting blood glucose and fasting insulin for HOMA estimates;
- Review/Dispense diaries for each week for subjects to self-monitor fasting morning blood glucose;
- Self-monitored fasting morning blood glucose (finger-stick) recorded in the patient diaries 3 days weekly in the morning;
- Adiponectin test;
- AEs/SAEs assessment;
- Subjects will be administered morning treatment dose in clinic followed by a small snack after 30 to 45 minutes;
- Remind subjects to arrive fasting for Visit 7 in 4 weeks.

#### 3.4.5 Visit 7 (Week 8, Days 56±4)

Subjects will report to the clinic in the morning following a 10-hour fast prior to taking morning medication. The following procedures will be performed:

- Review of concomitant medication;
- Measurement of weight;
- Collection of unused ORMD-0801 medication;
- Dispense 2 bottles of ORMD-0801 medication with instructions for administration. Subjects will receive either 8 mg ORMD-0801, 1 capsule twice a day (once in the morning approximately 30 to 45 minutes prior to breakfast and no later than 10 AM, and once at night between 8 PM to Midnight and no sooner than 1 hour after dinner) or matching placebo;
- Perform medication compliance check;

- Measurement of vital signs (SBP/DBP, heart rate and oral temperature);
- Collection of fasted blood samples for clinical laboratory evaluations (see [Section 6.5.5.1](#) for a complete list of tests performed):
  - Serum Chemistry including liver function tests (LFTs) and blood lipids;
  - Hematology;
- Measurement of fasting blood glucose and fasting insulin for HOMA estimates;
- Review/Dispense diaries for each week for subjects to self-monitor fasting morning blood glucose;
- Self-monitored fasting morning blood glucose (finger-stick) recorded in the patient diaries 3 days weekly in the morning;
- Adiponectin test;
- AEs/SAEs assessment;
- Subjects will be administered morning treatment dose in clinic followed by a small snack after 30 to 45 minutes;
- Remind subjects to arrive fasting for Visit 8 in 4 weeks.

#### 3.4.6 Visit 8 (Week 12, Days 84±4)

Subjects will report to the clinic in the morning following a 10-hour fast. The following procedures will be performed:

- Review of concomitant medication;
- Complete physical exam;
- Measurement of weight;
- Collection of unused ORMD-0801 medication;
- Perform medication compliance check;
- Measurement of vital signs (SBP/DBP, heart rate and oral temperature);
- Collection of fasted blood samples for clinical laboratory evaluations (see [Section 6.5.5.1](#) for a complete list of tests performed):
  - Serum Chemistry including liver function tests (LFTs) and blood lipids;
  - Hematology;
- Measurement of fasting blood glucose and fasting insulin for HOMA estimates;
- Review/Dispense diaries for each week for subjects to self-monitor fasting morning blood glucose;
- Self-monitored fasting morning blood glucose (finger-stick) recorded in the patient diaries 3 days weekly in the morning;
- Adiponectin test;
- HbA1c;
- CAP-Fibroscan;
- MRI-PDF;F;
- AEs/SAEs assessment;
- Remind subjects to arrive fasting for Visit 9 in 4 weeks.

### **3.5 End-of-Study (EOS) Phase (Visit 9, Week 16, Days 112±4)/Early Termination**

The EOS Visit (Visit 9) will be conducted 4 weeks following the last scheduled treatment Visit. Subjects will report to the clinic in the morning following a 10-hour fast. The following procedures will be performed:

- Review of concomitant medication;
- Complete PE, only if the investigator deems it necessary;
- Measurement of weight;
- Collection of unused ORMD-0801 medication;
- 12-Lead ECG, only if the investigator deems it necessary;
- Measurement of vital signs (SBP/DBP, heart rate and oral temperature), only if the investigator deems it necessary;
- Fasted blood samples will be collected for clinical laboratory evaluations (see [Section 6.5.5.1](#) for a complete list of tests performed):
  - Serum Chemistry including liver function tests (LFTs) and blood lipids;
  - Hematology;
- Measurement of fasting blood glucose and fasting insulin for HOMA estimates;
- Review/Collect subject diaries for self-monitored fasting morning blood glucose;
- HbA1c;
- Adiponectin test;
- AEs/SAEs assessment.

Patients who are discontinued early from the study will complete the EOS evaluations at the time of early discontinuation.

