
Summary of Assessments
	
Safety Assessments: Safety will be assessed by monitoring adverse events including hypoglycemia, physical exam, vital signs (blood pressure (SBP/DBP), heart rate and oral temperature), ECG and clinical laboratory assessments.
 
Efficacy Assessments: Efficacy will be assessed by measuring the final and baseline differences in fat content obtained from MRI-PDFFF results.

Duration of Participation
	
Screening Phase: up to 42 days prior to the Treatment Phase Placebo Run-in Phase: 2 weeks Treatment Phase: 12 weeks End-of-Study (EOS) Phase: 4 weeks after completion of the Treatment Phase

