## Table 1 Footnotes

-  Prior and concomitant medications will be reviewed at Screening. Concomitant medications will be reviewed through Visits 2-9.
-  Only if investigator deems necessary.
-  Height measurement and BMI calculation will be performed at Screening only. Weight will be measured as indicated.
-  Serum pregnancy test will be performed at Screening (Visit 1). Urine pregnancy test will be performed at Visit 2 and Visit 3.
-  Blood samples taken prior to dosing in clinic and snack provided after 30-45 minutes at Visit 2, 3, 6, and 7.
-  Study medication will be dispensed and collected at Visits 2-8 and collected at End-of-Study/Early Termination Visit.
-  Vital signs (blood pressure, heart rate, oral temperature). Vital signs will be measured in the sitting position after at least 5 minutes of rest.
-  Serum Chemistry: Sodium, Potassium, Glucose, BUN, Creatinine, BUN/Creatinine, Chloride, Calcium, Protein, Albumin, Globulin (total), A/G Ratio, SGOT (AST), SGPT (ALT), Bilirubin (total), Alkaline Phosphatase, CO2, Creatine Phosphokinase (CPK), Total cholesterol, LDL, HDL, Triglycerides, Thyroid Stimulating Hormone (TSH, screening only). Hematology: Hemoglobin, Hematocrit, RBC, WBC (total count and differential count), Platelets Count, Mean Platelet Volume (MPV), MCV, MCH, MCHC, RDW, Neutrophils (absolute value and %), Bands (ABS CNT), Bands, Lymphocytes (absolute value and %), Monocytes (absolute value and %), Eosinophils (absolute value and %), Basophils (absolute value and %), RBC Morphology. Urinalysis is not performed in this study.
-  Fasting blood glucose and insulin will be used to determine Homeostasis Model Assessment (HOMA) estimates. During an Unscheduled Visit only fasting blood glucose will be collected, if investigator deems necessary.
-  Self-monitoring (finger-stick) of fasting blood glucose will be required 3 days weekly in the morning, before breakfast, and recorded in patient diaries.
-  HCV-Ab (hepatitis C virus antibody), HBsAg (surface antigen of the hepatitis B virus), HBcore-total (total hepatitis B core antibody), HBs Ab (hepatitis B surface antibody), anti-HIV Ab (human immunodeficiency virus antibody).

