### 6.5.3 Physical Examination

A complete physical examination will be performed at Screening and Visits 3 and 8 (refer to [Table 1](#)). At the Investigator's discretion, an additional physical exam may be performed during the End-of-Study/Early Termination (Visit 9). The physical examination will include the following organ or body system assessments: skin; head, eyes, ears, nose, and throat; thyroid; lungs; cardiovascular; abdomen (liver, spleen); lymph nodes; and extremities, as well as an abbreviated neurological examination.

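### A dosed subject who withdraws before Visit 8 has no required post-dose physical exam and no required exit vital signs, because Early Termination shares the optional list written for Visit 9

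*Combined protocol and SAP*

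**What the plan says.** The Synopsis names both procedures among the assessments behind the primary safety endpoint: "Safety will be assessed by monitoring adverse events including hypoglycemia, physical exam, vital signs".

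The required physical exams are set in Section 6.5.3: "A complete physical examination will be performed at Screening and Visits 3 and 8". Required vital signs fall at Screening and at Visits 2 to 8 (Table 1 and the visit lists in Sections 3.2 to 3.4).

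Section 3.5 covers Visit 9 and Early Termination with a single list. For the exam it says "Complete PE, only if the investigator deems it necessary", and for vital signs "Measurement of vital signs (SBP/DBP, heart rate and oral temperature), only if the investigator deems it necessary". It then applies the list to early leavers: "Patients who are discontinued early from the study will complete the EOS evaluations at the time of early discontinuation". Table 1 has one shared End-of-Study/Early Termination column, in which exam and vital signs appear in parentheses with footnote 2: "Only if investigator deems necessary". Section 6.5.3 also leaves an exam at that visit to the investigator's discretion. Section 4.3 sends withdrawn subjects back to Section 3.5, so no other early-termination list exists.

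The overview in Section 3.1 is worded more loosely: "A complete physical exam and ECG will be performed and vital signs (SBP/DBP, heart rate and oral temperature) will be measured if deemed necessary", followed by a reference to the investigator.

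**The concern.** One list serves two different situations. For a completer, Visit 9 follows a Visit 8 at which exam and vital signs were required, so an optional repeat is reasonable. For a subject who leaves during treatment, the exit visit stands in for Visit 8, and there the same option means that neither assessment has to be made.

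The early leavers matter for safety. The reasons for termination in Section 4.3 include adverse events, intercurrent illness and unacceptable risk. Dosed subjects who leave are not replaced, and they stay in the safety population (Sections 4.3 and 8.1.1). Section 8.2.3 summarizes vital signs and their change from baseline, Section 8.2.5 lists exam findings by visit, and Section 8.2.7 rules out substitution of missing safety data, so whatever is not measured at exit is lost. If exit measurements are taken only when something is suspected, those on file are a selected set: normal values tend to go unrecorded, and an unsuspected change in blood pressure or heart rate is not found.

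**Working it through.** The plan states no figure for this point. The check is a cross-reading of the schedule, with simple arithmetic for scale.

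**Step 1: what is required, by time of exit after the first randomized dose**

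| Exit | Required post-dose exam | Required post-dose vital signs | Required exit vital signs |
|---|---|---|---|
| After the Visit 3 dose, before Visit 4 | None | None | None |
| From Visit 4 on, before Visit 8 | None | At each of Visits 4 to 7 attended | None |
| After Visit 8, before Visit 9 | Visit 8 | Visits 4 to 8 | None, but Visit 8 is done |

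Two entries rest on the order of procedures at Visit 3.

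- *Vital signs.* Section 6.5.2 puts them before any blood draw at the same time point, and Table 1 footnote 5 puts the Visit 3 draw before dosing. Visit 3 vital signs are therefore pre-dose.
- *Exam.* Section 3.4.1 lists the exam before the in-clinic dose, but no passage expressly labels it pre-dose. That it precedes dosing is an inference from list order.

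**Step 2: what remains required at Early Termination (Section 3.5)**

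Weight, serum chemistry with liver tests and lipids, hematology, fasting glucose and insulin, HbA1c, adiponectin, diary review, concomitant medication review and adverse event assessment carry no condition. Only the exam, the ECG and vital signs do.

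**Step 3: how many subjects**

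Inputs from Section 8.1: up to 36 randomized, about 30 to complete.

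- Non-completers: 36 − 30 = 6
- Share: 6/36 = 16.7%

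All six would have to be dosed and leave before Visit 8 to fall in the gap. The documents do not give the timing of loss, so the range is 0 to about 6.

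**Step 4: age of the last required vital signs at exit**

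Inputs from Table 1: Visit 6 on day 28, Visit 7 on day 56, Visit 8 on day 84, each ±4 days.

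- Nominal gap, Visit 6 to 7: 56 − 28 = 28 days
- Nominal gap, Visit 7 to 8: 84 − 56 = 28 days
- Window extremes: (56 + 4) − (28 − 4) = 36 days, and (84 + 4) − (56 − 4) = 36 days

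For an exit between Visits 6 and 8 the last required reading is thus up to 28 days old nominally. The 36 days need both windows at opposite limits and an exit just before the next visit.

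**The case against.** The strongest case on the other side is that the loss is small and that stronger readings go beyond the text. Four such readings are tempting.

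- *Early leavers get no end-of-treatment safety assessment.* A reader might infer this, but Step 2 shows otherwise. Anyone who reaches Visit 4 also has required on-treatment vital signs. Subjects stopped under the glucose rules of Section 3.7 continue with the remaining visits (with the qualifier that this be possible, in the high-glucose case) and can still reach Visit 8. Subjects withdrawn for a suspected drug-related event are followed to resolution or stabilization (Section 4.3).
- *Six subjects are expected to be affected.* The six may include subjects who leave after Visit 8, who were never dosed, or who never return. Six is a ceiling.
- *A planned comparison between arms is broken.* None is planned. Vital signs are summarized descriptively and exam findings are listed. With at most about six early leavers, complete exit data would not support a comparison either.
- *Section 3.1 contradicts Section 3.5.* The sentence can be read as requiring the exam and leaving only vital signs optional. It can equally be read with the condition covering everything, which agrees with Section 3.5, Table 1 and Section 6.5.3. It is ambiguous, not a contradiction.

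It is also fair to say that the study is exploratory and that an investigator may examine a departing subject anyway. All of this limits the size of the point. It does not remove it: the required exit items do not measure blood pressure or heart rate and do not replace an exam, and discretion does not give uniform data.

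**Conclusion.** The point holds in a limited form. Under Section 3.5, Table 1 and Section 6.5.3, a dosed subject who withdraws from the study before Visit 8 has no required post-dose physical exam and no required exit vital signs. Only a subject who leaves before Visit 4 has no required post-dose vital signs at all.

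The number affected is 0 to about 6 of 36 (at most 17%). The upper end assumes that every non-completer is dosed and leaves before Visit 8. The statement about the exam also assumes that the Visit 3 exam precedes the dose, as the list order suggests. Subjects who stop the drug but stay in follow-up are outside the point.

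This is not a fatal flaw. It is worth correcting because both procedures are named assessments of the primary safety endpoint, and exit data taken only on suspicion are selective.

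**What to change.** Split the shared End-of-Study/Early Termination column of Table 1, and separate the two situations in Sections 3.5 and 6.5.3 in the same way. At Early Termination, make vital signs and the complete physical exam required for subjects who have not had Visit 8. At Visit 9 for completers, leave both to the investigator's judgement as now. Reword the Section 3.1 sentence so that it says the same and can be read in only one way.

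The cost is a schedule and wording amendment, plus a few minutes of site time for the few early leavers who attend. They are already asked to come for weight, fasting blood samples and adverse event review, so there is no new visit and no new type of procedure. The change does not help with subjects who never return, for whom Section 4.3 promises only reasonable efforts.
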